- 2. Patients with Type 1 diabetes and non-painful diabetic peripheral neuropathy (DPN)
- 3. Patients with Type 1 diabetes and without diabetic peripheral neuropathy (DPN).
- 4. Healthy control subjects matched for age, BMI, and gender.

Diabetes duration, HbA1c, insulin use, ethnicity, and co-morbidities will be matched between group 1, 2 and 3 to best ability.

Inclusion criteria:

- 1. Men and women minimum 18 years of age and maximum 70 years of age
- 2. Signed informed consent form
- 3. Diagnosed with diabetes type I (for group 1-3)
- 4. Diagnosed with DPN defined as a threshold above 25-volt biothesiometry or absent feeling on the big toe using 10g-monofilament. (for group 1-2)
- 5. Answered questionnaire: PainDETECT
- 6. Nothing abnormal on initial tests (group 4)
- 7. Accepted initial screening blood samples
- 8. MRI-compatible participant

Exclusion criteria:

1. Current or previous alcohol- or drug abuse

- 2. Abnormal screening blood samples
- 3. Not being able to understand Danish written and/or verbally
- 4. Not being able to corporate to examination (e.g. not being able to speak, suffering from senile dementia etc.)
- 5. Previous chemotherapy or intake of experimental medicine
- 6. Active HSV- or VZV-infection or known HIV
- 7. Known severe skin disease
- 8. Known neural damage or disease in the neural system (e.g. MS, Guillain-Barre etc.)
- 9. Critical limb ischemia defined as in current clinical consensus[63]
- 10. Allergy or intolerance to histamine or inability to make do without for one day
- 11. Pregnancy
- 12. Active cancer-disease

C. Assessment of Resources

The study will be conducted in collaboration with Steno Diabetes Center Northern Denmark (SDCN) and Department of Radiology, Aalborg University Hospital. SDCN has access to patients with diabetes and can provide the necessary premises.

The study will be conducted in collaboration with Center for Neuroplasticity and Pain (CNAP), Aalborg University and SDCN, who have the technical and financial resources needed to establish the setup and conduct the examinations. Furthermore, an experienced research Bio. Med. Lab. Technologist is signed for the project thereby, alongside the Ph.D.-students, ensuring trained personnel. The study is set for a long inclusion, but additional time is available if required, as the Ph.D.-students are employed until 31st of October 2022.

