The project is initiated by [name], Aalborg University and SDCN, and is supported economically by Steno Diabetes Center North Denmark and Aalborg University. The support is however limited to staff salary and purchase of smaller equipment.

D. Study Procedures

Diabetic patients will be recruited during their scheduled visit to the outpatient clinic of SDCN, Aalborg University Hospital. Healthy controls will be recruited based on the included diabetic population using relatives of diabetic patients, medical students, and people known by participating staff.

After the informed consent is obtained the screening of the participant will be executed. Afterwards the participant have to attend three different sessions as shown in appended flowchart. Each session includes different tests and the sessions will be ordered randomly, since they have no influence on each other. Moreover, a conventional nerve conduction test will be performed, however this test will be performed as per usual by the department of neurophysiology, as this is a standard examination for patients with neuropathy.

PainDETECT

PainDETECT is an English questionnaire validated for detecting neuropathic pain[64]. It has later been translated and validated in Danish[65], and will be given each participant alongside instructions after form of consent has been signed. The patients will answer the questionnaire individually and will need to complete this before any other examinations can be conducted, as this will help placing the patients in the correct group.

Estimated time: 5-15 min.

Clinical examination

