MRI scan, 3) whole brain diffusion tensor imaging (DTI) for assessment of microstructure and fiber tracts, 4) MR spectroscopy assessment of metabolite, 5) BOLD signal for microvascular function in central level and peripheral level, and 6) MRI neurography of the peripheral nerve fibers. Additionally, cuff occlusion procedure will be performed in the MRI scanner (cf. next section). Heart rate, respiration rate, will be recorded throughout the MRI scan.

Estimated time: 90 min

Cuff occlusion

During the BOLD-MRI a cuff occlusion procedure will be performed to investigate the microvascular function. A cuff will be mounted around the leg, proximal to the knee, and inflated (240 mmHg) for 5 minutes to reduce or blockage the blood flow in the lower leg.

Estimated time: 15 min

Cognitive Tests

A validated cognitive questionnaire will be performed to test the mild cognitive impairment and possible affected cognitive domains in the participants. Moreover, a cognitive task will be performed in the scanner in order to test the participants' cognitive psychomotor speed and memory.

Estimated time: 15-20 min

Vagus Test Procedure

A commercial available handheld device (Vagus[™], Medicus Engineering Aps, Aarhus N, Denmark) will be used to test the autonomic nervous system and hereby the autonomic neuropathy. The participant will hold the device during four steps, where the device will 1) measure the heart rate at rest, 2) measure the heart rate response from laying position to standing position, 3) measure the relationship between heart rate during expiration and inspiration, and 4) measure the heart rate conditions during exhalation with a resistance of 40mmHg and at rest.

Estimated time: 10-15 min

Blood samples

Blood samples will be taken after informed consent has been signed. Blood taken is estimated not to exceed 15 ml and will include:

Hgb, leukocytes and diff. counting, blood platelets, cobalamin, folate, sodium, potassium, creatinine, bicarbonate, CRP, ALAT, alkaline phosphatase, LDH, bilirubin, albumin, coagulation factors, vitamin D 1.25, Calcium-ion, TSH, HbA1c and M-component.

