The blood samples will be taken and handled as usual by the biochemical department and will be destroyed after usage. No biobank will be made. All samples will start being analyzed immediately (within 2h), however, some samples (like vitamin D) will take some time to analyze. All results will be available within 10-12 days but samples will always be destroyed as soon as the analysis has been initialized.

V. DATA COLLECTION

Patient data will be collected using the electronic patient journal (EPJ) after consent of the participant. Only patients with an active continuity of care at SDCN will be included (as well as healthy controls). The principle investigator is employed at SDCN as a medical doctor alongside one of the Ph.D.-students.

Data collected will include demographic data such as name, age, sex, weight, and height, and clinical information related to diabetes, such as type, duration, medication, complicating peripheral arterial disease, and status of complications. This to ensure correct grouping of the patients and to make sure that they meet the inclusion criteria.

VI. DATA ANALYSIS

A. Sample Size Considerations

The following sample size estimation is made on the ability to separate a group of diabetic patients without neuropathy from a group of diabetes patients with 'moderate' neuropathy. The calculations are based on published measurement of the sensory nerve action potential amplitude in nerve fiber conduction assessments[45]. Setting the significance level to 0.05 and the power to 0.8 results in a sample size estimation of 16 persons in each group. $n = \frac{15.7*\sigma^2}{d^2} = \frac{15.7*(4.7^2+7.5^2)}{(14.4-5.7)^2} = 16$. The study involves several experiment measures, but we expect that max 20% of the measures will be dropouts. The number of participants needed to be recruited in each group will therefore be $N = \frac{n}{1-dropout} = \frac{16}{0.8} = 20$. We want to compare four groups as defined in section IV.B. Study Population. The total number of participants will therefore be 80.

B. Statistical Methodology

The data will initially be analyzed by a series ANOVA test to compare each measurement between the four groups.

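### Education is not planned as a matching factor, a named data item or a covariate, although controls may include medical students and staff acquaintances, so cognitive and functional brain-MRI contrasts with group 4 can partly reflect education

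*Combined protocol and SAP*

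**What the plan says.** **Recruitment (IV.D, Study Procedures).** For patients: "Diabetic patients will be recruited during their scheduled visit to the outpatient clinic of SDCN, Aalborg University Hospital". For controls: "Healthy controls will be recruited based on the included diabetic population using relatives of diabetic patients, medical students, and people known by participating staff". Nothing says how many controls may come from each source.

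**Matching (IV.B, Study Population).** For group 4: "Healthy control subjects matched for age, BMI, and gender". For the diabetic groups: "Diabetes duration, HbA1c, insulin use, ethnicity, and co-morbidities will be matched between group 1, 2 and 3 to best ability". Education and occupation are in neither list, nor in the eligibility criteria.

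**Outcomes (IV.D, Cognitive Tests and Multi-Level MRI).** "A validated cognitive questionnaire will be performed to test the mild cognitive impairment and possible affected cognitive domains in the participants". In addition, "a cognitive task will be performed in the scanner in order to test the participants' cognitive psychomotor speed and memory". The MRI session also covers the structure, function and metabolism of the brain. The questionnaire is not named, so it is unknown whether its scoring corrects for education.

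**Data (V, Data Collection).** "Data collected will include demographic data such as name, age, sex, weight, and height". The list is illustrative. Education is not among the items it names.

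**Analysis (VI.B, Statistical Methodology).** Each measurement is first compared over the four groups by ANOVA, with no covariate named. Section VIII (Study Limitations) notes that psychosocial factors may affect PTT and QST thresholds, but does not mention control selection or education.

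**The concern.** Patients and controls are drawn from different frames. Patients attend a diabetes clinic, while controls come from patients' families, a medical school and the social circle of hospital and university staff. Students are by definition in higher education. That staff acquaintances are also more educated than the patients is plausible, but it is an inference.

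Education is a plausible determinant of scores on cognitive screening, speed and memory tests, and so of activity during a cognitive task in the scanner. If group 4 is better educated than groups 1-3, a difference on these measures could come from diabetes, from education or from both. Matching on age, BMI and gender does not balance education, and a larger sample does not remove a bias of this kind. Without a record of education, the analyst could neither examine nor adjust for the imbalance.

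At stake is how the group 4 contrasts on cognition and functional brain MRI are read. Peripheral measures such as nerve conduction or corneal microscopy are less plausibly affected.

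**Working it through.** **1. The plan's own figure.** Section VI.A takes a difference of 14.4 − 5.7 = 8.7 and SDs of 4.7 and 7.5:

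n = 15.7 × (4.7² + 7.5²) / 8.7² = 15.7 × 78.34 / 75.69 = 16.25, written as 16. Then 16 / 0.8 = 20 per group, and 4 × 20 = 80.

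The figure reproduces. It rests on diabetes without neuropathy against moderate neuropathy, a contrast that does not involve group 4. It supplies the group size used below and is not itself in dispute.

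**2. Inputs for the bias.** The documents give neither the share of controls per source nor any effect of education on the outcomes. Both are assumed:
- share of controls from students and staff acquaintances: 25% or 50%;
- advantage of those controls on the outcome because of education: 0.5 or 1.0 SD;
- no true effect of diabetes, and equal means in the three patient groups.

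Spurious difference δ = share × advantage:
- 0.25 × 0.5 = 0.125 SD
- 0.25 × 1.0 = 0.25 SD, and likewise 0.50 × 0.5 = 0.25 SD
- 0.50 × 1.0 = 0.5 SD

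**3. Rejection rate of the planned ANOVA.** With n = 20 in each of four groups and only group 4 shifted by δ, the noncentrality is λ = n × δ² × 3/4, on 3 and 76 degrees of freedom. The 5% critical value of F is 2.725.

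| δ (SD) | λ = 20 × δ² × 0.75 | Chance of p < 0.05 |
|---|---|---|
| 0 | 0 | 5.0% |
| 0.125 | 0.234 | 6.3% |
| 0.25 | 0.938 | 10.8% |
| 0.5 | 3.75 | 32.2% |

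With the 16 evaluable per group that the plan allows for, the last three rates are 6.1%, 9.5% and 25.9%.

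**4. One patient group against controls.** For a two-sided t test of 20 against 20, the noncentrality is δ / √(2/20). It gives 12.0% at 0.25 SD (noncentrality 0.791) and 33.8% at 0.5 SD (1.581), close to the ANOVA.

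**5. Another way to set the assumption.** Let δ = education gap (0.5 to 1.5 SD) × correlation of education with the outcome (0.2 to 0.5). Then δ runs from 0.10 to 0.75 SD and the ANOVA rate (20 per group) from 5.8% to 65.5%. A middle case of 1.0 × 0.3 = 0.30 SD gives 13.6%. The answer depends almost wholly on inputs that the documents do not contain.

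**The case against.** The strongest reply is that the exposed comparisons are secondary. The main endpoint in IV.A is sensitivity and specificity together with a comparison of methods, and cognition appears in no stated objective. A reader might infer that the objective on central nervous system changes is undermined. The documents do not support that. Section III frames the objective as changes related to neuropathy in patients with diabetes, and groups 1-2 against group 3 can address it within one clinic population, whatever the source of the controls. This stands, and it confines the point to contrasts with group 4.

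Relatives of patients are the first source named and may resemble the patients in education. Age matching, in a study open to ages 18 to 70, also limits how many students can serve. Both may make the bias small. Neither sets a limit on staff acquaintances or balances education.

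A reader might infer that education could never be adjusted for. That is too strong: the list in section V is illustrative, and education could be asked at any session. What holds is that nothing plans its collection or use.

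Two further inferences should be left aside. That staff acquaintances know the tests or the examiners is speculation. A pooled comparison of 60 patients with 20 controls would give higher rates (16.0% at 0.25 SD and 48.1% at 0.5 SD), but the plan contains no such test. Nor is there an argument here that education shifts structural MRI, diffusion imaging or spectroscopy.

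**Conclusion.** The point holds for group 4 against the diabetic groups on the cognitive questionnaire, the in-scanner task and functional brain MRI. As written, the plan leaves those contrasts open to confounding by education and provides no means of detecting or removing it. Contrasts among groups 1-3 do not depend on control recruitment.

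Neither the size nor the direction of the bias can be established from the documents. Under an assumed education-related difference of 0.125 to 0.5 SD, no true effect and 20 per group, the planned ANOVA would reject in about 6% to 32% of cases instead of 5%. At the low end the inflation is negligible. This is worth correcting because the correction is cheap and is most reliably made while participants are being seen. It does not threaten the main endpoint or the sample size.

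**What to change.** - **Section V:** add years of education to the data collected for all participants.
- **Section IV.B:** balance group 4 with the diabetic groups on education as far as feasible. This may mean limiting the number of students and staff acquaintances; excluding those sources altogether is not needed if balance is achieved.
- **Section VI.B:** include education as a covariate in the cognitive and functional brain-MRI contrasts with group 4.

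The cost is one data field, one covariate (75 instead of 76 residual degrees of freedom with 80 participants) and possibly slightly slower control recruitment. Section IV.C says that more time is available if required. Adjustment works only where education overlaps between the groups, so the covariate does not replace attention to balance at recruitment.

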
III. STUDY OBJECTIVES

To test Perception Threshold Tracking (PTT) and multi-level MRI as methods for early detection and grading of severity of neuropathy in patients with diabetes mellitus.

To use multi-level MRI for characterization of peripheral and central nervous system changes related to neuropathy in patients with diabetes mellitus.

To compare Perception Threshold Tracking (PTT) and MRI to methods of traditional clinical practice and established methods of clinical research like Corneal Confocal Microscopy (CCM) and Quantitative Sensory Testing (QST) as well as axon flair-mediated neurogenic vasodilation (AF).

To test reliability of different measurements of neuropathy.

A better understanding of the underlying neuropathy of diabetes and new methods for early, reliable detection of DPN could result in intensified treatment and prophylactic measures prolonging of the complicationfree period of diabetes mellitus. Ultimately, this could potentially result in fewer complications related to the diabetic foot, and maybe even prolonged overall-survival and reduced healthcare cost.

IV. METHODS

A. Study Design

This study is a prospective, observational, cross-sector study starting March 1, 2019 running until December 1, 2021. The study will be conducted on patients from Aalborg University Hospital. Participants will be informed about the trial both written and vocally and no changed in antidiabetic medication will be performed. The instruments will include Corneal Confocal Microscopy (CCM), Quantitative Sensory Testing (QST), axon flair-mediated neurogenic vasodilation (AF), handheld heart rate measurement device (Vagus[™]), cuff, and MRI, which are all established methods of clinical research. Furthermore, participants will be tested using monofilament and Biothesiometry, which equals actual clinical practice, and with Perception Threshold Tracking (PTT), which is a new take on an older, well-known technology. Further tests will include a handheld pinprick device, measurements of peripheral arterial disease (PAD) and conventional NCS. The main endpoint of the study will be sensitivity/specificity of all examinations, as well as a comparison of the newer methods against more well-established modalities.

B. Study Population

The study population include four well-defined groups of subjects:

- 1. Patients with Type 1 diabetes and painful diabetic peripheral neuropathy (DPN).

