This mainly include biothesiometry and 10g-monofilamnent as these simple measures equals current clinical standard when screening for neuropathy. In biothesiometry, the detection limit of vibration is determined with slow rising strength until the patient perceives the vibration. In 10g-monofilament testing the physician uses a thin nylon fiber, which bends at a pressure of 10 grams. The filament is applied to four specific spots at the bottom of the foot. The tests are usually conducted during the scheduled visit to the outpatient clinic. If not, these tests will be performed just after inclusion before other experimental tests. This point also includes measurements of blood pressure measured at the arm, leg and toe as well as oxygen pressure in the blood vessels of the toe (TPO₂). This allows a good assessment of potential PAD. Results from the clinical examination might be collected as a Neuropath Disability Score (NDS). Above mentioned examinations might be conducted at any of the later mentioned sessions (see appended flowchart).

Estimated time: 15-20 min (possibly partly conducted during already scheduled appointment).

512 mN pinprick

This is a small custom-made pinprick device based on standardized QST (see below) principles. The device functions much like the monofilament described above but differs since it has a sharp finish thereby activating not large- but small nerve fibers. This test is conducted either during the scheduled visit or just after inclusion in the study alongside clinical examination.

Estimated time: 5 min.

Conventional nerve conduction

Will be conducted by the department of Neurophysiology, Aalborg University Hospital, as "golden standard" for assessment of large nerve fiber function. The test is a standard clinical test and might already be conducted at the time of inclusion.

Estimated time: 30 min.

Corneal Confocal Microscopy

Corneal Confocal Microscopy (CCM) is a noninvasive method for studying of the human cornea in vivo. It is used in an increasing fashion for assessment of corneal small nerve fiber pathology as an expression of peripheral neuropathy[46]. Before examination, the eye of the participant will be anaesthetized using 0.4% benoxinate hydrochloride and Viscotears for front eye lubrication. The examination will be conducted by personnel trained by seasoned international operators.

Estimated time: 60 min.

Quantitative Sensory Testing

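### The visible text lets the leg and toe perfusion measurements follow the 240 mmHg cuff occlusion, so they may come too late to support the critical limb ischemia exclusion

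*Combined protocol and SAP*

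**What the plan says.** **Perfusion measurements.** Section IV.A lists them among the study tests: "Further tests will include a handheld pinprick device, measurements of peripheral arterial disease (PAD) and conventional NCS". Section IV.D, Clinical examination, describes them as "measurements of blood pressure measured at the arm, leg and toe as well as oxygen pressure" in the toe, and gives their purpose: "This allows a good assessment of potential PAD".

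**Their timing.** The same paragraph first deals with biothesiometry and monofilament, usually done at the outpatient visit: "If not, these tests will be performed just after inclusion before other experimental tests". It then brings in the pressures and TPO2, and closes with: "Above mentioned examinations might be conducted at any of the later mentioned sessions (see appended flowchart". The next subsection, on the 512 mN pinprick, also points to an early clinical examination: "This test is conducted either during the scheduled visit or just after inclusion in the study alongside clinical examination".

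**Session order.** IV.D says the three sessions are randomly ordered because they do not affect one another. The surviving flowchart caption in XII allows any order within 3 months.

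**The cuff.** Under IV.D, Cuff occlusion, a cuff above the knee is inflated to 240 mmHg for 5 minutes during the MRI scan, to reduce or stop blood flow in the lower leg.

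**Eligibility.** Exclusion criterion 9 in IV.B reads: "Critical limb ischemia defined as in current clinical consensus[63". IV.D places screening ahead of the sessions: "After the informed consent is obtained the screening of the participant will be executed". Section V adds that PAD and complication status are taken from the patient record.

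**The concern.** Cuff occlusion is the one study procedure that deliberately stops blood flow to the leg. Before it is done, one would want to know that the leg is adequately perfused. The protocol already plans the measurements that would show this, but its timing rule lets them come afterwards.

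The reason given for random ordering is that the sessions do not influence each other. That is reasonable for the test readings. It overlooks that a perfusion result can bear on whether the participant should be in the study at all. If the result arrives late, an ineligible participant may already have had the cuff and other tests. What is at stake is a small precaution for participants and cleaner application of one exclusion criterion. The comparison of diagnostic methods is not affected.

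**Working it through.** The plan states no figure on this point, so the check sets the timing rules side by side and asks whether any visible rule forces the perfusion measurements ahead of the cuff.

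**Step 1: does the early-timing rule bind the pressures and TPO2?** The sentence requiring tests before the other experimental tests follows biothesiometry and monofilament and comes before the vascular measurements are introduced. Its application to them is at most implied. Even if it applies, the closing sentence of the paragraph loosens it.

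**Step 2: does screening bind them?** Screening precedes the sessions, but no visible sentence puts the pressures or TPO2 in it.

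**Step 3: does session order bind them?** No. Order is random in IV.D and free in the flowchart caption.

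**Step 4: can the cuff come first?** Let M be the session with MRI and cuff, P the session holding deferred pressures, and X the third session. Assume that P is not M and that all orders are equally likely.

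| Order | Cuff before pressures? |
|---|---|
| M P X | yes |
| M X P | yes |
| X M P | yes |
| P M X | no |
| P X M | no |
| X P M | no |

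That is 3/6 = 50% of orders. The other placements give:

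- pressures done at the clinic visit or just after inclusion: 0%;
- pressures deferred to the MRI session itself: 0% to 100%, since order within the session is not stated.

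These percentages apply only to participants whose measurements are deferred. The documents do not say how often that happens, so this is not a rate for the study.

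**Step 5: is criterion 9 confined to known disease?** Exclusion criteria 7 and 8 are worded as known conditions, and criterion 6 refers to known HIV. Criterion 9 carries no such qualifier. A record check alone therefore does not clearly satisfy it, and the pressures and TPO2 are the only PAD measurements described.

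**Step 6: who remains exposed?** Screening and the record check should catch recognised disease. Healthy controls must have no abnormality on initial tests (inclusion criterion 6). Those tests are not defined, but the requirement probably narrows the gap to groups 1-3. What is left is a patient with unrecognised critical limb ischemia whose measurements were also deferred past the cuff.

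**The case against.** The strongest objection is that the timing sentence refers the reader to a flowchart that is not available for review. It may already place the pressures at screening or before MRI, and the surviving caption does not say which tests belong to which session. This stands. The point is about what the visible text permits, and it does not show that the plan lacks a safeguard. If the flowchart does fix the order, the IV.D sentence still reads more loosely and should be brought into line.

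Second, the safety argument rests on two inferences. The protocol does not say that these measurements are used to apply criterion 9, whose definition lies in a cited source, and it does not connect criterion 9 with the cuff. This also stands. Both inferences are reasonable given the stated PAD purpose of the measurements and what the cuff does.

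Third, screening, active clinic care and the record check already protect participants. They do for recognised disease, which is why the remaining gap is small.

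A reader might also infer more than the documents support:

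- **That the cuff is harmful.** IX.B lists discomfort and brief mild to moderate pain, and says no lasting effects are reported. It does not discuss participants with impaired limb perfusion, but that silence is not evidence of harm.
- **That patients with critical limb ischemia would be enrolled.** The text shows only that the study's own measurements need not be available before the cuff.
- **That group assignment is also at risk because the deferral covers biothesiometry and monofilament.** That reading conflicts with the earlier sentence of the same paragraph, and inclusion criterion 4 needs those two tests to define groups 1 and 2.
- **That late exclusions would erode the sample size.** The 20% allowance in VI.A is for dropout of measures, and IV.C says extra time is available. The documents give no basis for a loss of power.

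**Conclusion.** The point holds as a low-cost precaution, with medium confidence. As written, the visible text allows a 5-minute, 240 mmHg above-knee occlusion before the only described PAD measurements are available to support the critical limb ischemia exclusion.

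The number affected is probably very small and cannot be estimated from the documents. No harm is shown and the main result does not change. The conclusion assumes that:

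- the unseen flowchart does not already fix the order;
- the pressures and TPO2 are relevant evidence for criterion 9;
- impaired limb perfusion matters for the cuff.

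**What to change.** In IV.D, Clinical examination, take the arm, leg and toe pressures and TPO2 out of the allowance for later sessions. Require them to be measured, and criterion 9 confirmed, before the MRI/cuff session: preferably at screening, otherwise on the same day before the scan. Keep the order of the remaining sessions random and show the same position in the flowchart. If the flowchart already does this, only the IV.D sentence needs changing.

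The cost is one sentence and one flowchart line. No test is added, because the clinical examination is already planned at 15-20 minutes, and the analysis does not change. The downside is slightly less scheduling flexibility for participants whose clinic visit did not include these measurements.
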